24.1. Feasibility of recruitment

A total of approximately 400-450 male and female subjects will be randomized in the clinical trial over the course of 4 years. Enrolling this number of subjects is not unreasonable. In a recently completed study, each of the sites enrolled around 125 subjects within 2 years. Four of the sites were also involved in successfully enrolling the required number of subjects for the Donny et. al. study.¹⁴

24.2. Staff Effort

Each site will have approximately 2 full time staff dedicated to this study, which will be sufficient for recruitment, conducting study visits and other procedures. Principal Investigators at each site will be devoting ~10% effort to the project. Each site has a Medical Director that is available for review of medical histories, adverse events or other issues involving medical oversight.

24.3. Facilities

University of Minnesota: The study will be conducted at the University of Minnesota's Tobacco Research Programs housed at the Delaware Clinical Research Unit at [name]. [name] serves as the Director for this Program and [name] is the Medical Director. The shared space at the Delaware Clinical Research Units

includes waiting room with a receptionist, 7 physical exam rooms (two dedicated to the Tobacco Research Programs), 1 phlebotomy room, 5 interview rooms, 2 day-hospital rooms, an infusion room, 1 smoking laboratory with one way observation room, laboratory spaces for processing blood and urine, a locked medication supply room, locked protocol room for subject files, cubicles for data entry, management and analyses, locked supply storage and access to three conference rooms. Two restrooms are in the clinical space for urine collections. We have dedicated space, with key card access, containing ten -20 freezers. Equipment available includes vital sign and expired air CO and alcohol monitors. The study will also have access to all of the resources of the University of Minnesota for our use, as needed.

Duke University: The project activities will take place in the Center for Addiction Science and Technology (CfAST) founded and directed by [name] (PI) and located in the Lakeview Plaza building adjacent to the Duke University and VA Medical Centers in Durham, NC. The PI has over 1300 square feet of laboratory space that includes two interview rooms, two physical exam rooms, a control room, three cognitive testing rooms, a scanner simulator room and a wet lab for conducting phlebotomy and biological specimen processing, and a dedicated sample storage room. In addition, the laboratory has two rooms equipped with a ventilation system that allows for indoor smoking. Finally, there is a secure room for medication storage and preparation. Equipment includes a computer system for electronic questionnaire administration (MediaLab), vital sign and expired air CO and alcohol monitors.

University of California-San Francisco: Research subjects are seen at the Tobacco Research Clinic located in San Francisco in close proximity to San Francisco General Hospital. The Clinic has a reception area and three private exam rooms for subject interviewing and specimen collection. The exam rooms are equipped with supplies to measure height, weight, blood pressure, expired CO, and breath alcohol levels. Additionally, two of the exam rooms have computers for administration of electronic questionnaires. There is a private bathroom for collection of urine samples. There is a lab where the specimens are prepared and equipment is housed. There are four separate rooms/offices where the clinical research coordinators and project manager are located and supplies are kept. A total of 9 separate computer stations are available for clinical research coordinator use. Additionally, the site has 2 laptops available for staff use. This is an off-site leased space located at [name].

Wake Forest University: The study will be conducted at the Wake Forest Tobacco Control Center of Excellence housed at the Biotech Place in Winston-Salem, NC. [name] serves as the Director for this Center. The space at the Wake Forest Tobacco Control Center of Excellence includes a waiting room with a receptionist, 7 ventilated testing rooms for smoking studies with audio and visual system for observation, 1 phlebotomy room, locked protocol room for subject files, cubicles and offices for data entry, management and analyses, locked laboratory space for product storage including 2 product refrigerators, 1 large wet laboratory space containing 2 -80 freezers and space for biosample processing, a conference room, and men's and women's restrooms adjacent to the suite for biosample collection. Equipment available includes vital sign and expired air CO and alcohol monitors. The study will also have access to all of the resources of the Wake Forest School of Medicine for our use, as needed.

Brown University: Research participants are seen at the Addictive Behaviors Research Laboratory at Center for Alcohol and Addiction Studies (CAAS), a 4800 square feet in size and was renovated per our specifications for the purpose of conducting human laboratory studies. The CAAS lab space contains 18 observation rooms, a room equipped for conducting physical examinations, a workroom for the storage and analysis of biological samples and a bathroom for participants' use. The CAAS lab is located in Brown University's Public Health building in downtown Providence, RI.

University of Pennsylvania: Research participants are seen at the Center for Interdisciplinary Research on Nicotine Addiction (CIRNA) Perelman School of Medicine at the University of Pennsylvania. The laboratory includes five 10x10 rooms equipped with exhaust fans and viewing windows to observe participants. Comfortable chairs placed in each. Restroom facilities are available for urine collection and there is a lab area for processing samples. Necessary equipment includes CO monitors, vitals monitors, laptop and desktop computers, and two refrigerators dedicated to specimen storage and two refrigerators dedicated to study product. The laboratory is located in Philadelphia.

24.4. Availability of Medical or Psychological Resources

Each site has a Medical Director and other study designated medical professionals, including access to a licensed psychologists that can be contacted if needed. Each site has specific Standard Operating Procedures that describe procedures to follow in case of emergency such as a suicidal participant. The medical staff will be trained in the study protocol, inclusion-exclusion criteria, and the conditions that may require temporary discontinuation of the study products or withdrawal from the study.

25. Conduct of the Study

25.1. Good Clinical Practice

The study will be conducted in accordance with the appropriate regulatory requirement(s). Essential clinical documents will be maintained to demonstrate the validity of the study and the integrity of the data collected. Master files will be established at the beginning of the study, maintained for the duration of the study and retained according to the appropriate regulations.

25.2. Ethical Considerations

The study will be conducted in accordance with ethical principles founded in the Declaration of Helsinki. The IRB will review all appropriate study documentation in order to safeguard the rights, safety and well-being of the subjects. The study will only be conducted at sites where IRB approval has been obtained. The protocol, consent, written information given to the subjects, safety updates, annual progress reports, and any revisions to these documents will be provided to the IRB by the investigator.

25.3. Record Retention

The investigator will retain study records including source data, copies of case report form, consent forms, HIPAA authorizations, and all study correspondence in a secured facility for at 7 years after the study file is closed with the IRB and FDA.

26. Subject Identifier

The subject identifier is an alpha-numeric combination. Example: E-B001 would be University of Minnesota's first subject.

Project Identifier: F= CENIC 2 Project 1

Site Identifier:

B = University of Minnesota

C = Brown University

E = University of Pennsylvania

F = Duke University

H = University of California – San Francisco

M = Wake Forest University

Subject ID:

B001-300

C001-300

E001-300

F001-300

H001-300

M001-300

Data Collection Time Point Identification Numbers:

94= Screening Visit

93=Baseline Visit 1

92=Baseline Visit 2

91=Marketplace Visit 1

00=Marketplace Visit 2 and Randomization

01= Week 1 visit

02= Week 2 visit

03= Week 3 visit (discontinued in conversion to telehealth visits)

04= Week 4 visit

06= Week 6 visit

08= Week 8 visit

10= Week 10 visit

12= Week 12 End of Intervention visit

16= 30 day follow-up visit

Additional visit (AV1, AV2, etc.)

86 = Termination Visit

27. Procedure Table	Platform	SCRN 94	BL 93	BL 92	MP 91	MP 00	Week 1-3 ³	Week 4	Week 6	Week 8	Week 10	Week 12	Follow -Up 16	Early Term
			Phase 1		Phase 2		Phase 3							
Phone Recruitment Questionnaire	REDCap	X												
VISIT ASSESSMENTS														
Weight (Height at screen)	Paper and REDCap	X	X	X	X	X	X	X	X	X	X	X	X	X
Pregnancy Test (if applicable)	Paper and REDCap			X		X		X		X		X		X
Heart Rate & BP	Paper and REDCap	X	X	X	X	X	X	X	X	X	X	X	X	X
Cotinine check, if needed	Paper and REDCap	X												
Breath Alcohol Test ⁴	Paper and REDCap	X	X	X	X	X	X	X	X	X	X	X	X	X
Urine Toxicology ⁴	Paper and REDCap	X											X	
Concomitant Medications	Paper and REDCap	X	X	X	X	X	X	X	X	X	X	X	X	X
Health Changes Questionnaire	Paper and REDCap			X	X	X	X	X	X	X	X	X	X	X
Adverse Events Assessment	Paper and REDCap			X	X	X	X	X	X	X	X	X	X	X
Product Accountability Log	Paper and REDCap				X	X	X	X	X	X	X	X		X
Procedures & Compliance Review	Paper				X	X	X	X	X	X	X	X	X	
End of Visit Evaluation	Paper and REDCap	X	X	X	X	X	X	X	X	X	X	X	X	X
SCREENING QUESTIONNAIRES														
Tobacco Use History and Exposure & Cessation Methods	Paper and REDCap	X												
Identifying Information	Paper and Access	X												
Demographics for Registration	Paper and REDCap						X							
Demographics	EDC	X												
Brief Medical History	Paper and REDCap	X												
PHQ PrimeMD (Beck if applicable)	Paper and REDCap	X												
CES-D	EDC	X					X		X		X		X	X
Beck Depression Inventory/GAD (if + PHQ or Elevated CES-D)	Paper and REDCap	X	X	X	X	X	X	X	X	X	X	X	X	X
(MINI) Suicide Subscale	On Paper only	X												
Drug Abuse Screening Test (DAST)	EDC	X												
Alcohol Use Questionnaire 12 mo	EDC	X												
Drug Use Questionnaire 12 mo	Paper and REDCap	X												
Michigan Alcohol Screening (SMAST)	EDC	X												
Assessment Name	Platform	SCRN 94	BL 93	BL 92	MP 91	MP 00	Week 1-3 ³	Week 4	Week 6	Week 8	Week 10	Week 12	F-Up 16	Early Term

Assessment Name	Platform	SCRN 94	BL 93	BL 92	MP 91	MP 00	Week 1-3 ³	Week 4	Week 6	Week 8	Week 10	Week 12	F-Up 16	Early Term
TOBACCO USE MEASURES														
Daily Call (IVR-tobacco diary)	IVR		X	X	X	X	X	X	X	X	X	X		X
Timeline Follow-back	Paper and REDCap		X	X	X	X	X	X	X	X	X	X	X	X
IVR Review	Paper and REDCap		X	X	X	X	X	X	X	X	X	X	X	X
ADVERSE CONSEQUENCES														
MNWS	EDCs		X	X	X	X	X	X	X	X	X	X		
QSU- Usual cigarettes	EDC		X	X	X	X								
QSU - Study cigarettes	EDC						X	X	X	X	X	X		
Alcohol Use Questionnaire 1 mo.	EDC		X			X		X		X		X		X
Drug Use Questionnaire - 1 month	Paper and REDCap		X			X		X		X		X		X
Respiratory & Global Health Quest.	EDC		X	X	X	X	X	X	X	X	X	X	X	X
DEPENDENCE MEASURES														
Cigarette Dependence Scale (FTND, PATH items, WISDM subscale)	EDC		X			X		X		X		X	X	X
Vaping/Product Dependence Scale	EDC												X	X
Severson SLT Dependence Scale													X	
Contemplation Ladder	EDC			X		X								
ACCEPTABILITY MEASURES														
Cigarette Eval. Scale Usual brand	EDC		X	X	X	X							X	X
Cigarette Eval. Scale Study cigs	EDC						X	X	X	X	X	X		X
Product Eval. Scale (all selected)	EDC				X	X	X	X	X	X	X	X		X
Perceived Health Risk Rating	EDC			X		X							X	
Cigarette Purchase Task - Usual Cigs	EDC			X		X							X	
Cigarette Purchase Task - Study Cigs	EDC												X	
Product Purchase Task - All products	EDC			X		X							X	
Assessment Name	Platform	SCRN 94	BL 93	BL 92	MP 91	MP 00	Week 1-3 ³	Week 4	Week 6	Week 8	Week 10	Week 12	F-Up 16	Early Term

Assessment Name	Platform	SCRN 94	BL 93	BL 92	MP 91	MP 00	Week 1-3 ³	Week 4	Week 6	Week 8	Week 10	Week 12	Follow -Up 16	Early Term
Biomarker Modifiers														
Dietary Intake	EDC		X			X		X		X		X		X
Environmental Tobacco Exposure	EDC		X			X		X		X		X		X
OTHER														
Social & Environmental Influences on Tobacco Use	EDC		X										X	
Product Expectancy Questionnaires	EDC			X										
Expected Utility (ANDS)			X											
End of Study Questionnaire	EDC												X	X
EXPOSURE BIOMARKER AND RISK FACTORS														
Carbon Monoxide	Paper and REDCap	X	X	X	X	X	X	X	X	X	X	X	X	X
Total Nicotine Equivalents (1 st void urine)	BMW Database &Excel*		X	(X*)		X		X		X		X	X	X
Total NNAL (1 st void urine)	BMW Database &Excel*		X	(X*)		X		X		X		X		X
Mercapturic acids of acrolein, benzene, crotonaldehyde, & acrylonitrile (1 st void urine)	BMW e Database &Excel*		X	(X*)		X		X		X		X		X
8-epi-PGF (1 st void urine)	BMW Database &Excel*		X	(X*)		X		X		X		X		X
Spot Urine or Saliva for compliance testing	BMW Database &Excel*						X	X	X	X	X	X		X
Nicotine Metabolite Ratio (saliva)	BMW Database &Excel*		X											
Genotyping (saliva)	BMW Database &Excel*			X										
Assessment Name	Platform	SCRN 94	BL 93	BL 92	MP 91	MP 00	Week 1-3 ³	Week 4	Week 6	Week 8	Week 10	Week 12	Follow -Up 16	Early Term

¹ Administered if early termination is within visit window; ² Samples may be used if subject was on study cigarettes at early termination visit; ³Visit 3 was discontinued in the COVID-19 amended telehealth procedures; ⁴Procedure was discontinued in the COVID-19 amended telehealth procedures* Banked and analyzed if needed.

28. References

1. Centers for Disease Control and Prevention. Cigarette smoking among adults -- United States, 2000. *MMWR Morb. Mortal. Wkly. Rep.* 2002;51(29):642-645.
2. Shafey O, American Cancer Society. *The Tobacco Atlas*. Atlanta, GA: American Cancer Society;2009. 9781604430134 (pbk. alk. paper).
http://www.ncbi.nlm.nih.gov/entrez/query.fcgi?cmd=Retrieve&db=PubMed&dopt=Citation&list_uids=19240228
http://www.ncbi.nlm.nih.gov/entrez/query.fcgi?cmd=Retrieve&db=PubMed&dopt=Citation&list_uids=10465828

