5.2.2. Phase 1: Baseline Procedures for Baseline Visits 1 (93) and 2 (92)

During Phase 1 of baseline (screening up to access to tobacco marketplace), eligible subjects will continue to smoke their preferred brand as usual. At the baseline clinic visits, subjects will complete several measures and provide biomarker samples as described below.

A. *Physiological Measures at Baseline (93 and 92):*

- 1) BrAC, which must be below 0.03 g/210L. If over the 0.03, the visit will be delayed until the level drops within range or subject can be rescheduled. If above 0.05, the visit will be rescheduled. Multiple baseline elevated BrAC results may result in discontinuation of the subject at the PI discretion. (BrAC was discontinued in conversion to telehealth visits.)
- 2) Expired breath CO level.
- 3) Vitals signs (blood pressure, heart rate).
- 4) Weight.
- 5) First morning void urine collected.
- 6) Saliva samples:
 - a) Saliva sample obtained with Salivette (with citric acid preparation) to be used for nicotine metabolite ratio (NMR) Visit 1 (93) only.
- 7) Spot urine for pregnancy tests [hCG detection] will be performed for female participants of childbearing potential (not surgically sterilized or 2 years post-menopausal) at Week

92 prior to offering Marketplace. (Pregnancy tests are performed on first morning void after conversion to telehealth visits.)

B. Questionnaires and Assessments at Baseline (93 and 92):

B.1 Web-based data collection program completed by the subject:

- 1) Minnesota Nicotine Withdrawal Scale (MNWS).
- 2) Questionnaire of Smoking Urges- Brief - Usual Brand Cigarette (QSU).
- 3) Cigarette Evaluation Scale – Baseline (CES – Usual Brand).
- 4) Respiratory and Global Health Questionnaire.
- 5) If monitored for psychiatric illness: Beck Depression Inventory 2nd Edition (BD-II) (paper only).
- 6) Cigarette Dependence Measures (Usual Brand - Visit 93 only).
- 7) Environmental Tobacco Smoke Exposure Questionnaire (Visit 93 only).
- 8) Social and Environmental Influences on Tobacco Use (Visit 93 only).
- 9) Dietary Intake (e.g., charred and smoked meats and fish) (Visit 93 only).
- 10) NIAAA Alcohol Use Questionnaire - 1 month version (Visit 93 only).
- 11) Expected Utility (ANDS) (Visit 93 only).
- 12) Perceived Health Risk of no tobacco use, usual brand cigarettes, very low nicotine cigarettes, smokeless tobacco/snus/nicotine pouches, medicinal nicotine, ENDS (Visit 92 only).
- 13) Product Expectancy Questionnaire (Visit 92 only).

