6.4. Analysis of Biomarkers

The following panel of biomarkers has been selected to represent exposures to relevant toxicants.

Biomarkers of Carcinogen Exposure: Biomarkers include urinary NNAL (metabolite of NNK, a potent lung cancer carcinogen), mercapturic acid metabolites of acrolein, benzene, crotonaldehyde, and acrylonitrile. These biomarkers have shown good laboratory reproducibility, have clear differences in levels between smokers and nonsmokers and/or decrease upon tobacco cessation, and reflect differences in toxicants in the various tobacco/nicotine products.^{52,53}

Oxidative damage: Urine samples will be banked for analysis of 8-iso-PGF2 α and will be conducted if supplemental funding is received. If no funding is available the samples will be banked for sharing.

Total nicotine equivalents (TNEs): This is the molar sum of nicotine and its metabolites. TNE accounts for 73-96% of the nicotine dose and is a useful measure of daily nicotine exposure.

Nicotine metabolite ratio (NMR): NMR will be assessed from saliva as an indicator of CYP2A6 enzymatic activity and is the ratio between two nicotine metabolites, free cotinine and *trans*-3'-hydroxycontinine (3-HC). Because CYP2A6 is the primary enzyme associated with nicotine metabolism and also catalyzes the conversion of cotinine to 3-HC, the 3-HC:cotinine ratio is considered to reflect the enzymatic activity of CYP2A6 and therefore the extent of nicotine clearance rate (higher the ratio, the faster the clearance rate). This metabolite ratio has been observed to be moderately correlated to CYP2A6 genotype and highly correlated with the rate of nicotine metabolism.⁵⁴⁻⁵⁹

Genotyping sample: A saliva sample will be collected for potential genotyping for genes related to metabolism of tobacco constituents, behavior, mood, brain functioning and harmful effects of tobacco exposure. Subjects may opt out of this collection and still be allowed to participate in the study. If the subject decides to withdraw their samples during or after the study, the samples will be destroyed immediately.

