5.2. Secondary Endpoints

- Biomarker: percent change in biomarker, CEMA, at the weeks 4, 8 and 12 visits during Phase 3 as compared to the last visit in Phase 2.
- Study cigarettes per day (CPD): the mean of study cigarettes smoked per day based on 7 days' Daily IVR-Revised data before the week 12 visit.
- Seven-day abstinence: if total CPD=0 for all 7 days before the week 12 visit and CO \leq 6ppm at week 12.

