5.3. Exploratory Endpoint

- Non-combusted tobacco/nicotine products use: the number of days using any non-combusted tobacco/nicotine products in Phase 3.
- Characteristics' of products chosen (type, flavor, nicotine strength).
- Biomarkers: percent change in biomarkers (Total Nicotine Equivalents, total NNAL, mercapturic acids at the weeks 4, 8 and 12 visits during Phase 3 as compared to the last visit in Phase 2).
- Product satisfaction (Product Evaluation Scale if they used the product since the last visit; Cigarette Evaluation Scale if they smoked cigarettes since the last visit).
- Perceived health risk (Phase 1, Phase 2 and end of week 12 of Phase 3: all products for all subjects).
- Measures of discomfort/dysfunction: MNWS-R, QSU, CESD (NNC vs VLNC cigarettes irrespective of use of products).
- Dependence (FTND, WISDM, PATH items; monthly for study cigarettes).

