6.4. Secondary Endpoint Analysis

The secondary endpoints will first be summarized by treatment group using mean and standard deviation. We will use similar adjusted regression methods for the secondary endpoints as for the primary endpoints described in Section 6.3.2. Details are described as follows.

- For the percent change (relative to the measure at the end of Phase 2) of the biomarker measured repeatedly (weeks 4, 8, 12), we will use linear mixed effects models (Verbeke and Molenberghs, 2000). Fixed effects in the model will include: treatment group, visit, treatment group by visit interaction, study site, whether the visit time is pre-COVID or not (as a time-dependent covariate), and any baseline characteristics (listed in Section 6.2) which are different at $p<0.20$. A random intercept for each subject will also be included in the model to account for within subject correlation.
- For study cigarette smoked, similar analyses to total cigarettes per day will be performed.
- For the abstinence outcome, we will use logistic regression.

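### The biomarker models adjust for no baseline biomarker value, and no analysis is specified for the Visit 93 CEMA, NNAL and other mercapturic acids, so precision can be gained by a change of SAP wording

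*Combined protocol and SAP*

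**What the plan says.** **Schedule.** In protocol Section 27, the first-void rows for TNE, total NNAL and "Mercapturic acids of acrolein, benzene, crotonaldehyde, & acrylonitrile (1 st void urine" have a plain X at Visit 93 and at Visit 00. Visit 92 has a bracketed, asterisked X, and the footnote reads "Banked and analyzed if needed". Protocol 5.2.2 lists "First morning void urine collected" for both Phase 1 visits. Protocol 3.3 treats CEMA as one of the mercapturic acids.

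**Reference visit.** SAP 5.2 defines the CEMA endpoint at weeks 4, 8 and 12 "during Phase 3 as compared to the last visit in Phase 2". SAP 5.3 uses the same reference for TNE, NNAL and the mercapturic acids. The last Phase 2 visit is Visit 00.

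**Model.** SAP 6.4 begins: "For the percent change (relative to the measure at the end of Phase 2) of the biomarker measured repeatedly (weeks 4, 8, 12". It then lists as fixed effects arm, visit, their interaction, site, COVID period, and any SAP 6.2 baseline characteristic picked up by a p-value screen. No baseline biomarker is on the fixed list. TNE is among the screened characteristics, taken from Phase 2; CEMA and NNAL are not. Protocol 16.6.4 gives the same structure, and SAP 6.5 applies it to the other biomarkers.

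**Use of Phase 1 urine.** The only named use is the safety endpoint for increased TNE (SAP 5.4).

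**The concern.** A single first-void sample is a noisy measure of a person's usual exposure. An unadjusted change score carries all of the noise in that sample into the outcome. The usual remedy is to put the baseline value into the model. The SAP does so for the primary endpoints (6.3.1) and for the repeated CPD model (6.3.2), where the adjusted analysis is expressly meant to improve efficiency, but not for the biomarkers. A second pre-randomisation measurement is also scheduled, and the plan gives it no role for CEMA, NNAL or the other mercapturic acids.

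CEMA is the only biomarker among the secondary endpoints, so it carries the hypothesis of lower toxicant exposure. No power is stated for it. What is at stake is the width of the confidence interval for that comparison. Its validity is not in question.

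**Working it through.** **1. The plan's own figures.** The documents give no power, SD or correlation for any biomarker. The only power figures are for the primary outcomes, and they serve here to confirm the evaluable number. With N = 400 and 20% attrition, n = 160 per arm. For smoke-free days, the control rate is 0.0504 and the other rate is 0.0504 + 11/84 = 0.1813. With one unit of exposure per subject, SE = √[(0.0504 + 0.1813)/160] = 0.0381. Then z = 0.1310/0.0381 − 2.241 = 1.20, so power is 0.885 (stated .88). The same formula gives .920 and .946 at N = 450 and 500 (stated .92 and .94). CPD power exceeds .99, as stated.

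**2. Does a plain X mean a scheduled assay?** Protocol 5.6.1 collects a first void at Week 16, yet the table marks only TNE there and leaves NNAL and the mercapturic acids blank. The marks are therefore analyte-specific. The diet and smoke-exposure questionnaires, which are the biomarker modifiers, are also scheduled at Visits 93 and 00 but not at 92. This supports a scheduled assay. It does not show that a result exists.

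**3. Variance of the arm contrast at one visit.** Assume the log scale, unit variance and a common correlation ρ between any two samples. Since ρ is not in the documents, 0.4 to 0.8 is shown.

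- Change from Visit 00, no covariate (the plan on the log scale): 2(1 − ρ)
- Visit 00 as covariate: 1 − ρ²
- Visits 00 and 93 as covariates: (1 − ρ)(1 + 2ρ)/(1 + ρ)

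Once Visit 00 is a covariate, it makes no difference to the arm contrast whether the outcome is the log value or the log change.

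| ρ | Plan | + Visit 00 | + both | Cut, Visit 00 vs plan | Cut, both vs plan | Further cut from Visit 93 |
|---|---|---|---|---|---|---|
| 0.4 | 1.20 | 0.84 | 0.771 | 30% | 36% | 8% |
| 0.6 | 0.80 | 0.64 | 0.550 | 20% | 31% | 14% |
| 0.8 | 0.40 | 0.36 | 0.289 | 10% | 28% | 20% |

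For scale, take an assumed effect of 0.3 SD, 160 per arm, two-sided α = 0.05 and ρ = 0.5. Power is .765 as planned, .873 with Visit 00 and .908 with both.

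**4. Unequal correlations.** Visit 93 reflects usual brand in the natural market. Visit 00 follows two weeks in the experimental marketplace and is closer to follow-up. Let a = r(93, week 12), b = r(00, week 12) and c = r(93, 00). The residual variance with both covariates is 1 − (a² + b² − 2abc)/(1 − c²). With assumed b = 0.6 and c = 0.7, Visit 00 alone leaves 0.640, and:

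| a | Both covariates | Further cut from Visit 93 |
|---|---|---|
| 0.60 | 0.576 | 9.9% |
| 0.50 | 0.627 | 2.0% |
| 0.42 (= bc) | 0.640 | 0% |
| 0.30 | 0.612 | 4.4% |

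The increment can vanish. As a covariate, Visit 93 costs at most one degree of freedom.

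**5. Raw percent change, as the SAP writes it.** I simulated lognormal values with equal correlation 0.4 to 0.8 and an assumed log SD of 0.5 to 0.9, with log covariates. Both covariates cut variance by 21% to 31% against the plan, and Visit 93's further share is 4% to 19%. The table in step 3 therefore applies only if the outcome itself is analysed on the log scale.

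**The case against.** **A baseline may be implied.** SAP 6.4 says its methods resemble those of 6.3.2, which adjust for baseline. But 6.4 then lists the biomarker model's fixed effects in full. That list matches the repeated CPD model except that baseline CPD has no biomarker counterpart, so as written there is none.

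**Assays are not proven.** A reader might infer that paid-for results are being thrown away. The documents do not support that. The 8-epi-PGF row has the same plain X marks, yet of that assay protocol 6.4 says "If no funding is available the samples will be banked for sharing". The asterisk also sits on the platform cell of each urine row, no assay cost is given, and the only payment shown is to participants for collection. This stands as a limit: the assay is scheduled, not shown to be done. It does not remove the point, because the funding condition is attached to that one analyte only. If the asterisk covered whole rows, it would also make the week 4, 8 and 12 CEMA values optional.

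**Visit 93 may be used elsewhere.** A reader might infer that every efficacy analysis ignores it. That goes too far. The exploratory GEE in SAP 6.5 relates product use to biomarkers without restricting the visits to Phase 3, and the multiple imputation in SAP 6.8 lists no variables. What can be said is that no use is specified.

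**Visit 00 is a legitimate reference.** It is the last value before randomisation and reflects marketplace conditions. This stands, and the reference should not change. Averaging the two visits would alter the endpoint's reference condition. It would also raise the variance by 18.8% in the least favourable case of step 4 (a = 0.30).

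**Conclusion.** The point holds as a gap in efficiency and specification. The planned comparison is unbiased, and so is the adjusted one, because both samples precede randomisation.

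At an assumed common log-scale correlation of 0.4 to 0.8, using both values as covariates cuts variance by 28% to 36% against the plan. A reader might credit that figure to Visit 93, but much of it, and most of it at low correlation, comes from entering Visit 00. Visit 93's own increment is 8% to 20% if the visits are exchangeable and 0% to about 10% under the unequal correlations tried. A sure gain from Visit 93 cannot be claimed, since the documents give no correlation. The case for Visit 00 is firm; the case for Visit 93 is that it costs almost nothing and may help.

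**What to change.** In SAP 6.4 and 6.5 (protocol 16.6.4 and 16.6.5):

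- Analyse each biomarker as log change from Visit 00, back-transformed to percent change, with Visit 00 kept as the reference.
- Enter log Visit 00 and, where assayed as scheduled, log Visit 93 together as fixed covariates. Under equal correlation, Visit 93 without Visit 00 adds nothing to a change score.
- If Visit 93 is missing, use Visit 00 alone. If Visit 00 is missing, the change is undefined, so handle it in the SAP 6.8 multiple imputation with Visit 93 as an auxiliary variable.
- State the purpose of the Visit 93 CEMA, NNAL and other mercapturic acid measurements.

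The cost is a few lines of wording, with no samples or procedures beyond those scheduled, and one or two degrees of freedom. The wording should be fixed before the biomarker data are analysed by arm.
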